- 2.1.1.9 At the time of registration: Patients must have recovered from the toxic effects of prior therapy: > 28 days from any investigational agent, > 28 days from prior cytotoxic therapy, > 14 days from vincristine, > 42 days from nitrosoureas, > 21 days from procarbazine administration, > 21 days from bevacizumab administration and > 7 days for non-cytotoxic agents, e.g., interferon, tamoxifen, thalidomide, cis-retinoic acid, etc. (radiosensitizer does not count). Any questions related to the definition of non-cytotoxic agents should be directed to Academic PI.
- 2.1.1.10 Patients must have adequate organ function:
- Bone marrow function (WBC $\geq 3,000/\mu l$, ANC $\geq 1,500/mm^3$, platelet count of $\geq 100,000/mm^3$, and hemoglobin $\geq 10 \text{ gm/dl}$).
 - o Eligibility level for hemoglobin may be reached by transfusion.
- Liver function (alanine amino transferase (ALT) and aspartate aminotransferase (AST) < 2.5 X ULN, and total bilirubin < 1.5 X ULN), prothrombin time (PT) or international normalized ratio (INR), and activated partial thromboplastin time (aPTT) ≤ 1.2 X ULN.

Version Date: 07/17/2025 Page 14 of 96

• Concomitant elevations in bilirubin and AST/ALT above 1.0 x ULN (upper limit of normal) are not permitted.

- O Subjects receiving anticoagulant therapy are eligible if their INR is stable and within the recommended range for the desired level of anticoagulation.
- Renal function (creatinine ≤1.5 mg/dL (133 μmol/L), or if > 1.5 mg/dL, calculated creatinine clearance ≥ 50 cc/min), and urine protein to creatinine ratio of < 1 prior to registration.
 - 2.1.1.11 Patients must have shown unequivocal radiographic evidence for tumor progression by MRI or CT scan as defined by Section 6.4.1.4.5. A scan should be performed within 14 days prior to registration and on a steroid dose that has been stable or decreasing for at least 5 days. If the steroid dose is increased between the date of imaging and registration a new baseline MR/CT is required. The same type of scan, i.e., MRI or CT must be used throughout the period of protocol treatment for tumor measurement.
 - 2.1.1.12 Patients having undergone recent resection of recurrent or progressive tumor will be eligible as long as all of the following conditions apply:
 - They have recovered from the effects of surgery and be > 28 days from surgery.

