- **Hold suspect drug until recovery to CTC Grade 0-1 (or to within 1 grade of starting values for pre-existing laboratory abnormalities), and then resume at same dose for topotecan or one dose level lower for pazopanib.
- ***Hold suspect drug until recovery to CTC Grade 0-1 (or to within 1 grade of starting values for pre-existing laboratory abnormalities), and then resume at same dose for topotecan or two dose levels lower for pazopanib.

3.3.6.1 Management of other drug related complications:

3.3.6.1.1.1 Management of Hepatic effects:

Cases of hepatic failure (including fatalities) have been reported during the use of pazopanib. In clinical trials with pazopanib, increase in serum transaminases (ALT, AST) and bilirubin were observed. In the majority of the cases, isolated increases in ALT and AST have been reported, without concomitant elevations of alkaline phosphatase or bilirubin. The vast majority (92.5%) of all transaminase elevations of any grade occurred in the first 18 weeks.

Monitor serum liver tests before initiation of treatment with pazopanib and at least once every 4 weeks for at least the first 4 months of treatment, and as clinically indicated. Periodic monitoring should then continue after this time period.

The following guidelines are provided for patients with baseline values of total bilirubin \leq 1.5 X ULN and AST and ALT \leq 2 X ULN.

- Patients with isolated ALT elevations between 3 X ULN and 8 X ULN may be continued on pazopanib with weekly monitoring of liver function until ALT return to Grade 1 (NCI CTCAE) or baseline.
- Patients with ALT of >8 X ULN should have pazopanib interrupted until they return to Grade 1 (NCI CTCAE) or baseline. If the potential benefit for reinitiating pazopanib treatment is considered to outweigh the risk for hepatotoxicity, then reintroduce pazopanib at a reduced dose of 400 mg once daily and measure serum

^{*}Except nausea/vomiting (unless patients are on optimal antiemetic therapy).

Version Date: 07/17/2025 Page 23 of 96

liver tests weekly for 8 weeks. Following reintroduction of pazopanib, if ALT elevations >3 X ULN recur, then pazopanib should be permanently discontinued.

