• If ALT elevations >3 X ULN occur concurrently with bilirubin elevations >2 X ULN pazopanib should be permanently discontinued. Patients should be monitored until return to Grade 1 (NCI CTCAE) or baseline. Pazopanib is a UGT1A1 inhibitor. Mild, indirect (unconjugated) hyperbilirubinaemia may occur in patients with Gilbert's syndrome. Patients with only a mild indirect hyperbilirubinaemia, known or suspected Gilbert's syndrome, and elevation in ALT >3 X ULN should be managed as per the recommendations outlined for isolated ALT elevations.

Concomitant use of pazopanib and simvastatin increases the risk of ALT elevations and should be undertaken with caution and close monitoring.

Beyond recommending that patients with mild hepatic impairment are treated with 800 mg pazopanib once daily (600 mg daily for this study) and reducing the initial starting dose to 200 mg per day for patients with moderate impairment, no further dose modification guidelines based on results of serum liver tests during therapy have been established for patients with preexisting hepatic impairment.

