13.2.18.2 Hepatic Impairment

The median steady-state pazopanib C_{max} and AUC(0-24) in patients with mild hepatic impairment (defined as either normal bilirubin and any degree of ALT elevations or as an elevation of bilirubin up to 1.5 x ULN regardless of the ALT value) after a once daily dose of 800 mg/day (30.9 μ g/ml, range 12.5-47.3 and 841.8 μ g.hr/ml, range 600.4-1078) are similar to the median in patients with no hepatic impairment (49.4 μ g/ml, range 17.1-85.7 and 888.2 μ g.hr/ml, range 345.5-1482).

The maximally tolerated pazopanib dose (MTD) in patients with moderate hepatic impairment (defined as an elevation of bilirubin > 1.5 x to 3 x ULN regardless of the ALT values) was 200 mg once daily. The median steady-state values of C_{max} (22.4 µg/ml, range 6.4-32.9) and AUC(0-24) (350.0 µg.hr/ml, range 131.8-487.7) after administration of 200 mg pazopanib once daily in subjects with moderate hepatic impairment were approximately 45% and 39%, respectively, that of the corresponding median values after administration of 800 mg once daily in subjects with normal hepatic function. There are insufficient data in patients with severe hepatic impairment (total bilirubin >3x ULN regardless of any level of ALT); therefore, use of pazopanib is not recommended in these patients.

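### Eligible patients with baseline AST or ALT above 2 and below 2.5 × ULN have no written permanent stop of pazopanib for ALT >3 × ULN with bilirubin >2 × ULN

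*Combined protocol and SAP*

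**What the plan says.** **Entry (2.1.1.10).** ALT and "aspartate aminotransferase (AST) < 2.5 X ULN, and total bilirubin < 1.5 X ULN" are required. The same item adds: "Concomitant elevations in bilirubin and AST/ALT above 1.0 x ULN (upper limit of normal) are not permitted". A patient with raised transaminases can therefore enter only with bilirubin at or below 1.0 × ULN.

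**Liver rules (3.3.6.1.1.1, repeated in 13.2.11.1).** The list opens with "The following guidelines are provided for patients with baseline values of total bilirubin" at most 1.5 × ULN and AST and ALT at most 2 × ULN. Under that opening come:
- isolated ALT of 3 to 8 × ULN: patients "may be continued on pazopanib with weekly monitoring of liver function until ALT return to Grade 1" or baseline;
- ALT above 8 × ULN: interrupt, with optional reintroduction at 400 mg and eight weeks of weekly tests; after that, "if ALT elevations >3 X ULN recur, then pazopanib should be permanently discontinued";
- the combined finding: "If ALT elevations >3 X ULN occur concurrently with bilirubin elevations >2 X ULN pazopanib should be permanently discontinued", with an exception for Gilbert's syndrome.

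Section 3.3.6.1.1.1 then closes by saying that, apart from the starting dose, "no further dose modification guidelines based on results of serum liver tests during therapy have been established for patients with preexisting hepatic impairment".

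**General rules, which apply whatever the baseline.**
- Table in 3.3.6: full dose at Grade 0–2 (hold optional if symptomatic); hold at Grade 3 or 4, then resume pazopanib one or two dose levels lower.
- 3.3.2: holds of up to 3 weeks.
- 3.3.6.14: Grade 1 or less to start a cycle, weekly evaluation if toxicity outlasts a one-week delay, and removal for another DLT at the reduced dose or for life-threatening toxicity.
- 3.7.1: removal for unacceptable toxicity or a delay beyond 21 days.
- 3.4.1.1: liver tests every 2 weeks twice, then every 4 weeks. Section 3.3.6.1.1.1 adds tests on clinical need, ahead of the scope sentence.

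**The concern.** The entry limit and the scope of the liver rules do not meet. Patients who enter between them have the highest transaminases the trial allows, yet the explicit combined stop is not written for them. Section 3.3.6.1.1.1 reports fatal hepatic failure on pazopanib, and the combined rise in ALT and bilirubin is one of only two liver findings for which that section orders permanent discontinuation. A site that followed the text could restart pazopanib after such an event without deviating from the protocol. What is at stake is the safety of a few individuals, not the trial's inference.

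**Working it through.** No power or error-rate figure is involved. The check compares two ranges and then looks for any other rule that covers the difference.

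1. **The band.** Eligible: AST and ALT <2.5 × ULN. Covered by the liver rules: AST and ALT ≤2 × ULN. The remainder is AST and/or ALT >2 and <2.5 × ULN, with bilirubin ≤1.0 × ULN because of the concomitant-elevation rule. The bilirubin limits leave no gap (entry <1.5, rules ≤1.5 × ULN).

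2. **Two patients side by side** (AST taken to be no higher than ALT).

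| | Enters at ALT 1.9 × ULN | Enters at ALT 2.3 × ULN |
|---|---|---|
| Eligible (<2.5) | yes | yes |
| Highest baseline bilirubin allowed | 1.0 × ULN | 1.0 × ULN |
| Within the liver rules (≤2) | yes | no |
| ALT rise needed to reach 3 × ULN | 3/1.9 = 1.58-fold | 3/2.3 = 1.30-fold |
| Written response to ALT >3 with bilirubin >2 × ULN | permanent stop | general toxicity rules |

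3. **What the general rules do with the combined event.** At Grade 3 or 4, pazopanib is held and then resumed lower: from 600 mg, to 400 mg (one level) or 200 mg (two levels). It is not resumed if the hold limits are exceeded or if the event is judged unacceptable, life-threatening or a repeat DLT. None of these rules names ALT or bilirubin. The CTCAE cut-points are not reproduced in the documents, so the grade of a given combined rise cannot be settled from them. If it were Grade 2, the table would keep full dose, with a hold optional if symptomatic, until the Grade 1 condition applied at the next cycle start.

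4. **Recurrent ALT.** Section 3.3.6.14 removes a patient with another DLT at the reduced dose. Section 9 counts attributable toxicities of Grade 3 or more and states its stopping boundary in DLTs. On that reading, a second attributable Grade 3 rise at the reduced dose already means removal. Only a recurrence above 3 × ULN but below Grade 3 escapes.

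5. **Weekly tests.** In the scoped list, weekly testing at ALT 3–8 × ULN is the condition for being allowed to continue. Patients in the band are not given that permission. They fall under the general holds, the weekly evaluation during a prolonged cycle delay, and testing on clinical need. Routine tests are otherwise every 4 weeks after the first two.

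6. **Size.** From baseline ALT of 2.0, 2.4 and 2.5 × ULN, the rise to 3 × ULN is 3/2.0 = 1.50, 3/2.4 = 1.25 and 3/2.5 = 1.20-fold. Bilirubin must also more than double (2/1.0 = 2.0). The share of patients in the band is not given: 1% × 66 = 0.66 patient, and an assumed 0–5% gives 0 to 3.3.

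**The case against.** The strongest reply is that these patients are not unprotected. General holds, removal rules and scheduled tests all reach them. At isolated ALT of 3–8 × ULN the general rules can be stricter than the liver list, which lets in-scope patients continue. Section 7.3.1 adds a teleconference every other week on each patient and review of adverse events by the principal investigator. The scope sentence does not say that its guidelines are for those patients only, and sensible investigators may apply the combined stop anyway. Section 2.1.2.18 excludes disease that would dangerously alter drug metabolism, which may thin the band. All of this stands, and it narrows the point. None of it supplies a written permanent stop for the combined event.

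Two stronger readings are tempting, and the documents support neither.
- A reader might infer that three safeguards are wholly absent, or that liver management is missing for this band. Steps 4 and 5 of the working show that the recurrence stop and the weekly testing are only partly missing.
- A reader might take the closing sentence on pre-existing impairment as proof that the band was deliberately left out. Section 13.2.18.2 describes mild impairment as "defined as either normal bilirubin and any degree of ALT elevations", among other forms. That takes in the patient entering at 1.9 × ULN as much as the one at 2.3, so it cannot separate them. The gap rests on the scope sentence alone.

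**Conclusion.** The point holds in a narrow form. For eligible patients with baseline AST or ALT above 2 and below 2.5 × ULN, nothing in the protocol requires permanent discontinuation on ALT >3 × ULN with bilirubin >2 × ULN, while the same finding ends pazopanib for a patient who entered at or below 2 × ULN (Gilbert's exception aside). This assumes that the scope sentence is read as written.

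The point is minor. The count of 0 to 3 patients rests on an assumed share, not on data. The combined event should be uncommon, since 3.3.6.1.1.1 says most transaminase rises occur without a bilirubin rise. The documents give no rate for it, so no probability is claimed. No endpoint, sample size or error rate is affected.

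**What to change.** Leave the scope sentence in place for the isolated-ALT items. Simply widening it would also extend the permission to continue at ALT 3–8 × ULN, which could loosen care for the patients of concern. Instead, add to both 3.3.6.1.1.1 and 13.2.11.1 that the following apply to all enrolled patients whatever their baseline:
- permanent discontinuation for ALT >3 × ULN with bilirubin >2 × ULN, keeping the Gilbert's exception;
- permanent discontinuation if ALT >3 × ULN recurs after any liver-related hold and reintroduction;
- weekly liver tests while ALT is above 3 × ULN.

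The addition should say that it takes precedence over the closing sentence on pre-existing impairment.

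The cost is a short insertion in two sections, a few extra liver tests, and possibly an earlier stop for a patient who enters near the limit: after reintroduction, a 1.25-fold rise from 2.4 × ULN already reaches 3 × ULN.

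The alternative is to lower the entry limit in 2.1.1.10 to AST and ALT ≤2 × ULN and update the eligibility checklist. That closes the gap at entry and should lose very few candidates.

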3.4 ON STUDY EVALUATION

3.4.1 General Requirements

- 3.4.1.1 CBC with differential and platelets and serum chemistries and LFTs (ALT, AST and bilirubin) will be performed every two weeks X 2, (+/- 3 days) then every 4 weeks (+/- 3 days) prior to each cycle during treatment. UPC (+/- 3 days) will be done monthly prior to each cycle.
- 3.4.1.2 A brain MRI/CT for group B will be done monthly until 3 months then every other month thereafter, for group A scan will be obtained every other month prior to initiation of odd numbered 28 days treatment cycles (+/- 3 days).
- 3.4.1.3 All relevant information regarding drug doses, concomitant medications, and doses, measurable lesions with measurements, tumor response, laboratory examinations, and treatment-related toxicities shall be documented in the patient's medical record and flow sheets.
- 3.4.2 A complete Neurologic exam (to include documentation of the patients Karnofsky Performance Status) will be performed prior to every evaluation where an MRI is scheduled. The MDASI-BT (Appendix 15.5) will be completed at baseline and at the time of each evaluation that includes an imaging study.
- 3.4.3 The patient will complete the MDASI-BT (see Appendix 15.5) at the time of clinical evaluation with MRI as long as the clinical therapy is being administered, unless clinical deterioration makes self-report not possible before that time. The time when patients are unable to complete the self-report questionnaires will be used as part of the study analysis. The MDASI-BT will be completed only by the patient, unless changes in vision

Version Date: 07/17/2025 Page 27 of 96

or weakness make this difficult. If this occurs, then the caregiver or research assistant may read the questions to the patient or assist with marking the severity number or score as described by the patient. A patient caregiver may complete the questionnaires as a patient-preference proxy if the patient's deficits preclude self-report.

- 3.4.3.1 A measurement of BP should be taken twice weekly for the first 2 months of therapy, then weekly for 2 months, and then once per month thereafter as detailed in 3.3.5.2. BP can be assessed by any method (i.e., at home or by another physician) as long as the treating physician is informed of the measurement, verifies any measurement that is not normal and takes appropriate action.
- 3.4.3.2 Thyroid function test (T4 and TSH) (+/- 3 days) are to be monitored every 8 weeks (+/- 3 days)

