3.6 STUDY CALENDAR

	Screening	Week	Week	Every 4	Every 8	End of	F/U ^m
		One	Two	wks	wks	tx	
Informed Consent	X						

Version Date: 07/17/2025 Page 28 of 96

	Screening	Week	Week	Every 4	Every 8	End of	F/U ^m
		One	Two	wks	wks	tx	
History/Physical Exam	X			X		X	
NeuroExam ^k	X				X		
Concomitant				X			
Meds/Adverse Events							
Vitals signs	X	Xa	Xa	X		X	
Performance Status	X			X		X	
Treatment Toxicity				X		X	
CBC ^g	X		X	X		X	
Chemistries, LFTs ^b	X		Xb	Xb		X	
Pregnancy test j	X					X	
UPC ratio	X			X			
UA	X						
Thyroid function test	X				Xc		
Coagulation test	X						
EKG ^d	X				Xd		
MRI or CT brain	X			Xe	Xf		
MDASI-BT ¹	X			X	X		
Tumor tissue	Xi						
Hepatitis Questionnaire	X						
Hepatitis B and C	Xn						

^a Monitoring of BP only: A measurement of BP should be taken twice weekly for the first 2 months of therapy, then weekly for 2 months, and then once per month thereafter. BP can be assessed by any method (i.e., at home or by another physician) as long as the treating physician is informed of the measurement, verifies any measurement that is not normal and takes appropriate action.

^b Monitoring of LFTs: LFTs (AST, ALT, Bili) every 2 weeks X 2, (+/- 3 days) then every 4 weeks prior to each cycle during treatment. (+/- 3 days)

^c Thyroid function test (T4 and TSH) are monitored every 8 weeks (+/- 3 days)

^dEKG: Week 4 and then every 8 weeks until end of treatment (+/-3 days)

^e MRI: Group B only: Every 4 weeks until 3 months, then every 8 weeks thereafter (+/- 3 days)

f MRI: Group A only: Scan will be obtained every other month prior to initiation of odd numbered 28 day treatment cycles (+/- 3 days)

^gCBC: Performed every 2 weeks X 2 (+/- 3 days) then every 4 weeks (+/3 days) prior to each cycle. For patients experiencing significant drop in WBCs or platelets felt related to Topotecan, CBCs should be obtained more frequently (weekly or more frequently) to assess timing for retreatment or need for G-CSF or transfusion support.

ⁱ Tumor tissue blocks or 15 unstained paraffin slides to be obtained from institutions where surgery performed and provided to collaborating neuro-pathologist for confirmatory tumor diagnosis. Patient may be enrolled prior to acquisition of tumor tissue block.

^J Only for women of childbearing potential; must be tested within 14 days prior to starting study drugs

Version Date: 07/17/2025 Page 29 of 96

- ¹ MDASI-BT should be completed by patient at the time of clinical evaluation with MRI.

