3.7 CRITERIA FOR REMOVAL FROM PROTOCOL THERAPY AND OFF STUDY CRITERIA

- 3.7.1 Criteria for Removal from Protocol Therapy
 - 3.7.1.1 After administration of 12 28-day cycles of treatment, unless further treatment is felt to be in the best interest of the patient by the treating physician.
 - 3.7.1.2 Progression of disease (as defined in Section **6.4.1**).

Patients must be followed by the same type of brain scan, as was used for baseline tumor measurements, and will be removed from study if progression is documented after any cycle of treatment. Patients with stable disease, partial or complete response will continue on therapy.

- 3.7.1.3 Unacceptable toxicity (see Section 3.3).
- 3.7.1.4 The patient may withdraw from the study at any time for any reason.
- 3.7.1.5 Medical or psychiatric illness which in the investigator's judgment renders the patient incapable of further therapy.
- 3.7.1.6 Treatment delay due to toxicity greater than 21 days measured from the start of the preceding cycle.
- 3.7.1.7 All reasons for discontinuation of treatment must be documented in the flow sheets

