6.4.1 Definitions of Response

- 6.4.1.1 Measurable Disease: Bidimensionally measurable lesions with clearly defined margins by CT or MRI scan.
- 6.4.1.2 Evaluable Disease: Unidimensionally measurable lesions, masses with margins not clearly defined.
- 6.4.1.3 Non-Evaluable Disease: Not Applicable for response evaluation
- 6.4.1.4 Objective Status, To Be Recorded at Each Evaluation: If there are too many measurable lesions to measure at each evaluation, choose the largest two to be followed before a patient is entered on study. The remaining lesions will be considered evaluable for the purpose of objective status determination. Unless progression is observed, objective status can only be determined when ALL measurable and evaluable sites and lesions are assessed.
 - 6.4.1.4.1 Complete Response (CR): Complete disappearance of all measurable and evaluable disease. No new lesions. No evidence of non-evaluable disease. All measurable, evaluable and non-evaluable lesions and sites must be assessed using the same techniques as baseline. Patients must be on no steroids.
 - 6.4.1.4.2 Partial Response (PR): Greater than or equal to 50% decrease under baseline in the sum of products of perpendicular diameters of all measurable lesions. No progression of evaluable disease. No new lesions. All measurable and evaluable lesions and sites must be assessed using the same techniques as baseline. The steroid dose at the time of the scan evaluation should be no greater than the maximum dose used in the first 8 weeks from initiation of therapy.
 - 6.4.1.4.3 Partial Response, Non-Measurable (PRNM): Not applicable.
 - 6.4.1.4.4 Stable/No Response: Does not qualify for CR, PR, or progression. All measurable and evaluable sites must be assessed using the same techniques as baseline. The steroid dose at the time of the scan

Version Date: 07/17/2025 Page 36 of 96

evaluation should be no greater than the maximum dose used in the first 8 weeks from initiation of therapy.

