- 6.4.1.4.5 Progression: 25% increase in the sum of products of all measurable lesions over smallest sum observed (over baseline if no decrease) using the same techniques as baseline, OR clear worsening of any evaluable disease, OR appearance of any new lesion/site, OR clear clinical worsening or failure to return for evaluation due to death or deteriorating condition (unless clearly unrelated to this cancer). Patients will also be considered to have progressive disease if there is significant increase in T2/FLAIR non-enhancing lesions AND clinical progression. (See section 6.4.1 and 6.3.7 for definitions). To be considered progressive disease, increase in T2/FLAIR should occur on stable or increasing doses of corticosteroids compared to baseline scan or best response following initiation of therapy, and should not be due to co-morbid events (e.g. radiation therapy, demyelination, ischemic injury, infection, seizures, post-operative changes, or other treatment effects).
- 6.4.1.4.6 Unknown: Progression has not been documented and one or more measurable or evaluable sites have not been assessed.
- 6.4.2 Best Response: This will be calculated from the sequence of objective statuses.

For patients with all disease sites assessed every evaluation period, the best response will be defined as the best objective status as measured according to Section 6.4.1. If the response does not persist at the next regular scheduled MRI, the response will still be recorded based on the prior scan, but will be designated as a non-sustained response. If the response is sustained, e. g. still present on the subsequent MRI, it will be recorded as a sustained response, lasting until the time of tumor progression. Best response is unknown if the patient does not qualify for a best response or increasing disease and if all objective status determinations before progression are unknown.

- 6.4.3 Neurological Exam: Although not used for determining response, it is useful to evaluate improvement in the neurologic exam, (as compared to the baseline assessment), that should coincide with objective measurement of tumor size.
 - +1 Better
 - 0 Unchanged
 - -1 Worse
 - B Baseline

Version Date: 07/17/2025 Page 37 of 96

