6.4.4 Performance Status: Patients will be graded according to Karnofsky Performance Status (See Appendix 15.1). Clinical progression can be declared if there is a decrease in 100 or 90 to 70 or less, at least 20 from 80 or less, or decline in KPS from any baseline to 50 or less, for at least 7 days and not attributable to comorbid events or change in steroid dose.

- 6.4.5 Time to Treatment Failure: From date of registration to the date of first observation of progressive disease (as defined in Section 6.4.1.4.5), non-reversible neurologic progression or permanently increased steroid requirement (applies to stable disease only), death due to any cause, or early discontinuation of treatment.
- 6.4.6 Time to Death: From date of registration to date of death due to any cause.
- 6.4.7 Documenting FLAIR: investigators will be asked to measure tumor related changes on FLAIR sequence as best as possible, as non-enhancing patterns of recurrence can occur. If this occurs within the setting of clinical progression not caused by seizures or other identifiable cause, the patient will be considered to have progressive disease. Please see section 6.4.1 for definition of clinical progression.

Presumed non-enhancing tumor without clinical progression should be observed. The time of progression if eventual clinical deterioration occurs can be back dated to the time of the increase in non-enhancing tumor. Investigators will also be asked to document if recurrence of disease is multifocal.

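### CT-only follow-up is allowed, yet the T2/FLAIR progression and back-dating rules need MRI, so a CT-followed patient's progression can be dated later; the effect on PFS3/PFS6 is one-directional, of unknown size and probably small

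*Combined protocol and SAP*

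**What the plan says.** **Where CT is allowed.** Eligibility criterion 2.1.1.11 fixes one modality for the treatment period: "The same type of scan, i.e., MRI or CT must be used throughout the period of protocol treatment for tumor measurement". Section 3.7.1.2 ties follow-up to baseline: "Patients must be followed by the same type of brain scan, as was used for baseline tumor measurements". The scan schedule in 3.4.1.2 is neutral on modality ("A brain MRI/CT for group B will be done monthly until 3 months then every other month thereafter"). So are the calendar row in 3.6 ("MRI or CT brain") and the definition of measurable disease in 6.4.1.1 ("Bidimensionally measurable lesions with clearly defined margins by CT or MRI scan"). None of these makes CT conditional on MRI being impossible.

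**Where MRI is needed.** Section 6.4.1.4.5 counts as progression a "significant increase in T2/FLAIR non-enhancing lesions AND clinical progression". Section 6.4.7 adds that "investigators will be asked to measure tumor related changes on FLAIR sequence as best as possible", because non-enhancing recurrence can occur. If clinical deterioration follows later, 6.4.7 lets the progression date be moved back to the time the non-enhancing tumor increased.

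**Where MRI is assumed.** Sections 3.4.2 and 3.4.3, calendar footnotes e and f, and the best-response rule in 6.4.2 speak of MRI only.

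**What uses the date.** The primary endpoint (6.4 and section 9) is the status at 6 months in Group A and 3 months in Group B. Group A is declared promising at 9 of 34 and Group B at 2 of 32.

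**The concern.** A patient with a CT baseline must stay on CT, and CT yields no T2 or FLAIR series. For that patient the T2/FLAIR route cannot be assessed as written, and there is no FLAIR scan date to go back to. The protocol gives no CT equivalent and does not say how such patients are classified or dated. Two patients with the same clinical course can then get different progression dates because of the scanner. With a landmark endpoint, a date that moves across 3 or 6 months changes the primary outcome. The direction is fixed: relative to MRI, CT can only delay the recorded date and so can only add to the progression-free count. Section 9 plans no record or separate look by modality.

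**Working it through.** **Step 1. What a CT-followed patient loses under the text.**

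- *Event status: little.* In 6.4.1.4.5 a separate route, joined by OR, is "OR clear clinical worsening or failure to return for evaluation due to death or deteriorating condition". It needs no scan. The T2/FLAIR route itself requires clinical progression, so a patient who meets it will ordinarily also meet the clinical route.
- *Non-enhancing growth without symptoms: nothing.* Under 6.4.7 this is observed and not called progression, on MRI as on CT.
- *The date: this is the loss.* On MRI, once deterioration occurs, the date may be moved back to the earlier scan. On CT there is no FLAIR finding to move it to.

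**Step 2. A course that changes the primary outcome.** Take a Group B patient whose non-enhancing tumor grows by the month-2 scan, who meets no other progression criterion by month 3, and who declines clinically after month 3. On MRI the date may go back to month 2, which is a failure at 3 months. On CT the date is that of the decline, which is a success. All four conditions are needed: growth before the landmark, no other route by the landmark, decline after it, and an investigator who would have back-dated.

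**Step 3. Reproduce the designs in section 9.** With stage-1 size n1, continuation bound r1, total n and final bound r:

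P(promising | p) = sum over x = r1..n1 of C(n1,x) p^x (1−p)^(n1−x) × P[Bin(n−n1, p) ≥ max(0, r−x)]

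- Group A (n1 = 9, r1 = 2, n = 34, r = 9): 0.0474 at 15%, 0.811 at 35%.
- Group B (n1 = 14, r1 = 1, n = 32, r = 2): 0.0287 at 1%, 0.801 at 12%.

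Both agree with the stated limits of 5% and 80%.

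**Step 4. Sensitivity on assumed inputs.** Let c be the CT share and b the back-dating share. The documents give neither. There are two ways to define b:

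- *Reading 1:* b is a share of all CT patients. The observed null rate is p0 + c·b.
- *Reading 2:* b is a share of the CT patients counted progression-free. If their observed rate is q, then p0 = q(1−b), so the excess is q − p0 = p0·b/(1−b). The observed null rate is p0 + c·p0·b/(1−b).

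Example, Group B at c = b = 10%. Reading 1: 0.01 + 0.10 × 0.10 = 0.02. Reading 2: 0.01 + 0.10 × 0.01 × 0.10/0.90 = 0.0101.

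| c, b | A, reading 1 | A, reading 2 | B, reading 1 | B, reading 2 |
|---|---|---|---|---|
| none | 0.047 | 0.047 | 0.029 | 0.029 |
| 5%, 5% | 0.052 | 0.048 | 0.043 | 0.029 |
| 10%, 10% | 0.067 | 0.050 | 0.097 | 0.029 |
| 20%, 20% | 0.151 | 0.061 | 0.370 | 0.031 |

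Entries are the probability of declaring promise when the rate under MRI dating is the null rate. At 10% and 10%, reading 1 corresponds to 0.10 × 0.10 × 32 = 0.32 expected patients in Group B and 0.34 in Group A. In Group B it also implies a CT success rate of 0.01 + 0.10 = 0.11, of which 0.10/0.11 = 91% would be due to the scanner. That is a demanding assumption.

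**The case against.** The strongest reply is that the scanner hardly affects whether progression is recorded. Clinical worsening alone is already an event, and symptom-free non-enhancing growth is only watched on either modality. Back-dating is permitted rather than required. The back-dating sentence refers to non-enhancing tumor, not to a FLAIR measurement. Section 6.4.1.4.5 also has a route through worsening of evaluable disease, which under 6.4.1.2 includes masses with unclear margins, so CT might pick up some of this growth. Group B is scanned monthly to 3 months, and the working text mostly expects MRI, so few patients may be on CT. Finally, requiring MRI still leaves CT for patients who cannot have it.

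Most of this stands, and it limits the size. It does not close the gap. CT-only follow-up is open to any patient, the FLAIR-based date is unavailable to those patients, and no sentence says how to date them. The request to measure FLAIR as well as can be done sets no rule for CT. The last point is right, and it is why the fix needs a dating rule for the CT patients who remain.

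**Conclusion.** The passages are not reconciled. The modality rules allow CT throughout, while one progression route and its dating rest on MRI sequences. The consequence is a possible later progression date for CT-followed patients, always in the direction of success at PFS3 or PFS6. If no patient is followed by CT, there is no effect.

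The size cannot be taken from the documents and is probably small. At 10% for both assumed shares, attained type I error is 0.050 to 0.067 in Group A and 0.029 to 0.097 in Group B. The upper ends need b to apply to every CT patient.

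Two stronger readings are tempting. One is that progression through non-enhancing disease cannot be captured at all on CT; the separate clinical route answers that. The other starts from an assumed CT share of 5–10%, which gives 1.6–3.2 of 32 patients, and infers that Group B's threshold of 2 could be met wholly by such patients. That treats every CT-followed patient as misclassified, whereas each would have to satisfy all the conditions in step 2. The documents do not support it.

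The point is still worth acting on, because it concerns the primary endpoint, runs one way and is cheap to settle.

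**What to change.** 1. In 2.1.1.11, 3.4.1.2 and the study calendar, make MRI with FLAIR the modality at baseline and follow-up, with CT only when MRI is contraindicated.
2. In 6.4.7, state how progression is classified and dated for patients followed by CT, including whether any back-dating applies to them.
3. Record the modality of each tumor assessment, and repeat the PFS6 and PFS3 counts without CT-followed patients. The bounds 9 of 34 and 2 of 32 belong to the full cohorts, so this count is a sensitivity analysis and not a second decision rule.

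The cost is small: wording in three places, one dating sentence, one data field and one extra count. The downside is that a site that would use CT for convenience must use MRI. If patients have already been enrolled, items 2 and 3 can still be applied to them.
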